**NCT number: NCT05293314**

**Document date: July 17, 2023**

## **Study Description**

To investigate whether the breath test is able to detect bronchiectasis using breathomics. This study was conducted with a prospective specimen collection, evaluator-blinded, case-controlled clinical study designed to evaluate the accuracy of breathomics to diagnosis of bronchiectasis in adults.

## **Study Design**

### **Study Population:**

The age of all subjects were all older than 18. The study population was recruited from Shanghai pulmonary hospital. Diagnosis of bronchiectasis was performed using chest HRCT scans in suspected patients with coughing and expectoration, or long durations of haemoptysis. Healthy participants were as control. Participants with Interstitial lung disease or Sarcoidosis were as unhealthy control.

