### **Criteria:**

#### **Inclusion Criteria:**

Patients were recruited according to the following inclusion criteria: (1) Age>18 years; (2) the diagnosis of BE was according to European Respiratory Society guidelines for the management of adult bronchiectasis; (3) Willing to join in and sign the informed consent form. Healthy control subjects were recruited according to the following inclusion criteria:(1) Age>18 years; (2) No history of any lung disease (according to pulmonary imaging and physical examinations); (3) Willing to join in and sign the informed consent form.

Unhealthy control subjects were recruited according to the following inclusion criteria: (1) Age>18 years; (2) The diagnosis of ILD was according to HRCT and clinical symptoms by two experts' consensus; (3) The diagnosis of Sarcoidosis (SA) was according to American Thoracic Society Clinical Practice Guideline;(4) Willing to join in and sign the informed consent form.

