#### **Exclusion Criteria:**

(1) Patients combined with serious comorbidities (chronic renal failure, hepatic disease, etc.); (2) Patients who are diagnosed with asthma, pneumonia, malignant tumor, and COPD; (3) Women who are pregnant or preparing for pregnancy or breastfeeding; (4) Participated in other clinical trials within three months; (5) Refused to join in and sign the informed consent form.

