## **Study plan**

### **To construct an easy, fast, and non-invasive VOCs-based bronchiectasis detection mode**

This study plans to recruit 200 Bronchiectasis patients diagnosed by HRCT from the Department of Respiratory and Critical Care Medicine of Shanghai Pulmonary Hospital and 200 healthy participants from July,2022 to March,2023.

The exhaled gas of admitted patients was collected on the day of admission, that of outpatients on the day of outpatient service, and that of examinees on the day of physical examination. After the exhaled gas was collected, VOCs were detected by mass spectrometry according to the standard processing flow, and the full spectrum of exhaled VOCs of Bronchiectasis patients and healthy people were analyzed to explore the characteristics of exhaled VOCs of Bronchiectasis patients and healthy people, Analyze the correlation between VOCs and clinical disease severity and prognosis (number of acute exacerbations) characteristics. The data of 400 cases were randomly assigned in a 5:2:3 ratio to the discovery cohort, internal validation, and blinded test cohorts. The discovery and internal validation sets were used for potential VOC biomarkers selection and diagnostic model construction.

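### The planned test set compares HRCT-diagnosed bronchiectasis with healthy examinees, so its specificity, accuracy and AUC cannot be assumed to hold for symptomatic patients under suspicion of the disease

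*Combined protocol and SAP*

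**What the plan says.** The Study Description calls this a "prospective specimen collection, evaluator-blinded, case-controlled clinical study designed to evaluate the accuracy of breathomics to diagnosis of bronchiectasis in adults".

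The Study Population section gives the only diagnostic setting in the document: "Diagnosis of bronchiectasis was performed using chest HRCT scans in suspected patients with coughing and expectoration, or long durations of haemoptysis". The same section adds a second kind of control: "Participants with Interstitial lung disease or Sarcoidosis were as unhealthy control".

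Under Inclusion Criteria, a case enters with an established diagnosis ("the diagnosis of BE was according to European Respiratory Society guidelines for the management of adult bronchiectasis"). A healthy control enters with "No history of any lung disease (according to pulmonary imaging and physical examinations"). ILD and sarcoidosis controls also enter by established diagnosis. The Exclusion Criteria remove "Patients who are diagnosed with asthma, pneumonia, malignant tumor, and COPD".

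The Study plan then sets the numbers: "This study plans to recruit 200 Bronchiectasis patients diagnosed by HRCT", plus 200 healthy participants. Breath is taken from patients on the day of admission or of the outpatient visit, and from examinees on the day of their physical examination. Both subsections of the Study plan divide 400 records 5:2:3 into discovery, internal validation and blinded test sets. The ILD/sarcoidosis group appears in neither subsection. The VOCs analysis section refers only to controls, without saying which. The Statistical analysis section reports sensitivity, specificity, accuracy and AUC.

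**The concern.** A diagnostic test is needed for people in whom the diagnosis is in question. Here those are patients with cough and sputum, or prolonged haemoptysis, who are sent for HRCT. In the 400, such patients appear only if their scan is positive; the people without the disease come from a different source, the physical-examination clinic. This is a two-gate design: cases and non-cases enter by separate routes.

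Case status is then mixed up with being a respiratory patient. The first feature-selection step keeps ions that differ between bronchiectasis and controls. If the controls are healthy, an ion raised by airway inflammation, sputum or general illness passes as readily as one specific to bronchiectasis. Blinding the evaluator and splitting the records at random do not help, because under the Study plan the test set repeats the contrast on which the model was built. At stake is whether a good specificity or AUC supports a statement about diagnosis, or only the narrower statement that bronchiectasis patients can be told apart from healthy people.

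**Working it through.** **1. The plan's own figures.** 200 + 200 = 400. A 5:2:3 split gives 400 × 0.5 = 200 for discovery, 400 × 0.2 = 80 for internal validation and 400 × 0.3 = 120 for the blinded test. If the classes stay balanced, the test set holds about 60 cases and 60 non-cases. Under the Study plan all 60 non-cases are healthy participants. The document gives no target accuracy, precision or power, so 400 cannot be derived any further.

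**2. Who has a place.**

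| Person | Defined group? | Among the 400? |
|---|---|---|
| Suspect, HRCT shows bronchiectasis | Case | Yes, 200 |
| Healthy examinee | Healthy control | Yes, 200 |
| Suspect, HRCT leads to ILD or sarcoidosis | Could be an unhealthy control | No number or role given |
| Suspect, HRCT shows none of these | None | No |
| Patient with asthma, pneumonia, malignant tumor or COPD | Excluded | No |

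The 200 healthy places fill the whole non-case half of the 400, so specificity rests on healthy people alone.

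**3. What a confidence interval would cover.** Suppose 57 of 60 test-set controls are classified correctly (an assumed result). Specificity is 57/60 = 95%, with exact (Clopper-Pearson) 95% limits of 86.1% to 99.0%. That interval reflects sampling error among healthy examinees. It contains no information about suspects.

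**4. How much it could matter: assumed illustration.** Take a model score that is normal with unit variance in each group, with cases shifted by *d* from healthy examinees. Assume sensitivity 0.90 and specificity 0.90 against healthy examinees. Then

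- *d* = z(0.90) + z(0.90) = 1.2816 + 1.2816 ≈ 2.56
- AUC = Φ(*d*/√2) = 0.965

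Let *s* be the share of that shift also present in symptomatic suspects without bronchiectasis. At the same cut-off:

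- AUC in suspects = Φ(*d*(1 − *s*)/√2)
- specificity in suspects = Φ(1.2816 − *d s*)
- accuracy with equal numbers of cases and non-cases = (0.90 + specificity)/2

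| *s* | AUC | Specificity | Accuracy |
|---|---|---|---|
| 0 | 0.965 | 0.90 | 0.90 |
| 0.25 | 0.91 | 0.74 | 0.82 |
| 0.50 | 0.82 | 0.50 | 0.70 |
| 0.75 | 0.68 | 0.26 | 0.58 |

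Sensitivity stays at 0.90 in every row, because the cases and the cut-off do not change. Neither the 0.90 values nor *s* comes from the document, and nothing in the plan collects the data that would estimate *s*.

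**The case against.** The design is openly labelled case-controlled, and comparing cases with healthy people is an ordinary first step. No intended-use population is stated either: the Study Description asks first whether breath can detect bronchiectasis, and that suspects are the target is inferred from the aim of diagnosis and the Study Population section. Both points stand. They make this a limit on interpretation, not a concealed error. They do not remove the mismatch between the claim and the sample.

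A reader might go further in several ways that the documents do not support.

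- *HRCT-negative suspects enter no group at all.* Too absolute. A suspect whose scan leads to ILD could become an unhealthy control, and a group of this kind partly addresses the worry about non-specific markers of illness. But the Study plan gives it no number or role, and its members are chosen by established diagnosis, not by suspicion of bronchiectasis.
- *Prospective specimen collection is a misdescription.* It is not. Breath is collected from enrolled participants on the day they attend, and the term does not imply that disease status is unknown. The document does not give the order of breath sampling and HRCT reading.
- *A question about cough would separate the two groups almost perfectly.* Healthy controls must have no lung disease on imaging and examination, but they need not be free of cough. No symptom data are given.
- *HRCT-negative suspects could be added at little cost.* The recruitment window was July 2022 to March 2023 and the document is dated July 17, 2023, so enrolment had probably closed. Suspects would also have to meet the eight-hour fast and the dietary limits of the night before. The exclusion of asthma, pneumonia, malignant tumor and COPD would still leave those alternative diagnoses out.

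**Conclusion.** The point holds as a restriction on what may be claimed. Specificity, accuracy and AUC from the blinded test set measure separation from healthy examinees. They cannot be assumed to apply to symptomatic suspects, and for them they are likely to be optimistic. Sensitivity is less affected, because the cases do come from symptomatic suspects.

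The direction is a judgement: it assumes that symptomatic patients without bronchiectasis share some of the breath signal that separates cases from healthy people. The size cannot be computed from the documents. The range from no loss to an AUC of 0.68 shows only how far the answer depends on an unknown share. It would be a mistake to read the table as an estimate, or to conclude that the figures are shown to be wrong for suspects; they are not estimated there at all.

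The conclusion rests on the Study plan's account of the 400. If the unhealthy controls were in fact meant to enter the split, the contrast would be wider than stated here, but suspects with no such diagnosis would still be missing.

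**What to change.** 1. In the Study Description and in the study's conclusion, restate the estimand. Suggested wording: *to evaluate how well exhaled-breath VOCs distinguish HRCT-confirmed bronchiectasis from healthy examinees in a two-gate case-control sample; specificity, accuracy and AUC are not estimates for patients under suspicion of bronchiectasis.* Keep the description of specimen collection as prospective.

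2. Reconcile Study Population and Inclusion Criteria with the two subsections of the Study plan on the unhealthy controls: how many there are, whether they belong to the 400, and whether they are used in model building, in testing or in neither. Say in VOCs analysis which controls are meant. If they are tested, report specificity against them separately from specificity against healthy examinees.

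Both changes are to wording and need no new data. The cost is a narrower and less favourable claim.

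For a follow-on validation study, recommend taking breath from consecutive suspects before the HRCT is read and assigning disease status afterwards. That is a new study with its own sample size and logistics, not a cheap amendment to this one.

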### **Criteria:**

#### **Inclusion Criteria:**

Patients were recruited according to the following inclusion criteria: (1) Age>18 years; (2) the diagnosis of BE was according to European Respiratory Society guidelines for the management of adult bronchiectasis; (3) Willing to join in and sign the informed consent form. Healthy control subjects were recruited according to the following inclusion criteria:(1) Age>18 years; (2) No history of any lung disease (according to pulmonary imaging and physical examinations); (3) Willing to join in and sign the informed consent form.

Unhealthy control subjects were recruited according to the following inclusion criteria: (1) Age>18 years; (2) The diagnosis of ILD was according to HRCT and clinical symptoms by two experts' consensus; (3) The diagnosis of Sarcoidosis (SA) was according to American Thoracic Society Clinical Practice Guideline;(4) Willing to join in and sign the informed consent form.

#### **Exclusion Criteria:**

(1) Patients combined with serious comorbidities (chronic renal failure, hepatic disease, etc.); (2) Patients who are diagnosed with asthma, pneumonia, malignant tumor, and COPD; (3) Women who are pregnant or preparing for pregnancy or breastfeeding; (4) Participated in other clinical trials within three months; (5) Refused to join in and sign the informed consent form.

### **Exhaled Breath collection:**

All exhaled breath samples were collected by trained investigators following the same protocol. All participants were asked to fast for eight hours and rinsed their mouths with clean water before collecting breath samples. To reduce potential confounding factors, all participants were asked to not ingest spicy food, alcohol, or coffee the night before exhaled breath collection. Participants were asked to perform a single deep nasal inhalation followed by complete exhalation via their mouth into an airbag with a volume of 1.2L made of polyether-ether-ketone (PEEK) bags until the bags were full of exhaled air. For each day of sample collection, ambient air was collected to make sure the environment was not polluted. The PEEK airbags were carried out to the laboratory within one week and analyzed by HPPI-

TOFMS analysis.

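### Sampling occasion follows participant type and the daily ambient air has only a stated pollution-check use, so a setting difference, if one exists, could enter the blinded test AUC undetected

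*Combined protocol and SAP*

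**What the plan says.** Sampling occasion is set in the Study plan, under the heading on constructing the detection model. For patients it reads: "The exhaled gas of admitted patients was collected on the day of admission, that of outpatients on the day of outpatient service". The third group named there is sampled at a health check, not a clinical visit: "and that of examinees on the day of physical examination". The cases come from the respiratory department. The examinees are read here as the healthy controls, which fits the way Clinical Data Collection describes the people surveyed at health examinations.

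Exhaled Breath collection describes the manoeuvre: "Participants were asked to perform a single deep nasal inhalation followed by complete exhalation via their mouth into an airbag". It gives room air a single purpose: "For each day of sample collection, ambient air was collected to make sure the environment was not polluted". The sections on VOCs detection, VOCs analysis and Statistical analysis do not mention ambient air. VOCs detection says that peak areas are normalised, but not how.

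The 400 cases are split at random 5:2:3, and the models are judged against the HRCT diagnosis in the blinded test part.

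Some provisions reduce the scope for a difference. Study Population names one hospital. Exhaled Breath collection applies one procedure to everyone ("All exhaled breath samples were collected by trained investigators following the same protocol"), with common fasting, mouth-rinse and diet rules.

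**The concern.** If cases and healthy controls were sampled in different rooms, some ions could differ between the groups because the inhaled air differs. Feature selection keeps ions that differ between groups, whatever the cause. A holdout set protects against overfitting, and blinding protects against evaluator bias. Neither protects against a difference that is present in discovery, validation and test alike. A pollution check asks whether the air is acceptable; two acceptable rooms can still differ in trace ions.

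The main accuracy result is at stake. Taken alone, the test AUC against healthy controls would not separate a setting signal from a disease signal. The plan already collects samples that could help separate them, but states no analysis that does so.

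**Working it through.** **The plan's own figures.** 200 cases + 200 healthy = 400. The 5:2:3 split gives 200/80/120, or on average 100 vs 100 in discovery and 60 vs 60 in the test set. No power calculation, target AUC or ambient data are given, so every shift below is an assumption.

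**Simple formula.** Suppose there is no disease effect and *k* independent ions are each shifted by *d* SD between settings. With all *k* ions known and equally weighted, AUC = Φ(d√k/√2). For k = 10:
- d = 0.2: Φ(0.447) = 0.673
- d = 0.3: Φ(0.671) = 0.749
- d = 0.5: Φ(1.118) = 0.868

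The planned process must first find those ions among 300, so realised values are lower.

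**Simulation.** 300 normal ions, ten shifted by setting with common correlation ρ, no disease effect, discovery 100 vs 100, test 60 vs 60. All ρ lie below the plan's 0.9 filter. RF is the planned chain: Mann-Whitney p<0.05, correlation filter, random forest ranking, top ten, random forest model (40 repetitions, standard error about 0.01). LR takes the ten smallest p-values and fits a ridge logistic regression (500 repetitions). Mean test AUC:

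| Shift | Method | ρ=0 | ρ=0.3 | ρ=0.5 | ρ=0.7 |
|---|---|---|---|---|---|
| 0.5 SD | RF | 0.778 | 0.639 | 0.604 | 0.572 |
| 0.5 SD | LR | 0.806 | 0.670 | 0.632 | 0.610 |
| 0.3 SD | RF | 0.593 | 0.538 | 0.525 | 0.514 |
| 0.3 SD | LR | 0.605 | 0.562 | 0.547 | 0.535 |
| 0.2 SD | LR | 0.534 | 0.526 | 0.520 | 0.516 |

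With no shift, LR gives 0.498. The number of shifted ions also matters. With a simpler mean-difference score and independent ions, going from 10 to 30 shifted ions moves the AUC from 0.54 to 0.59 at 0.2 SD, from 0.61 to 0.70 at 0.3 SD, and from 0.82 to 0.87 at 0.5 SD. None of these runs models the plan's unstated normalisation.

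**With a real disease signal.** Ten disease ions at 0.5 SD give a random forest AUC of 0.757 without a setting shift. Adding a 0.5 SD setting shift in ten ions gives 0.829 (ρ=0) or 0.790 (ρ=0.5), an inflation of 0.072 or 0.033.

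**Would a same-setting comparison discriminate?** Assume 60 patient controls who share the cases' setting and have no effect on these ions. With logistic regression and a 0.5 SD shift, a pure setting signal gives 0.497-0.504 against them. With real disease ions the AUC is 0.796 (no shift), 0.708 (shift, ρ=0) or 0.782 (shift, ρ=0.5). The comparison therefore separates the two explanations, if such controls exist.

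**The case against.** The strongest reply is that nothing in the documents shows a difference in setting. There is one hospital, one collection protocol and trained collectors, and normalisation may remove some offsets. All of this stands. One hospital does not mean one room, however. The common protocol standardises participant and procedure without saying that it standardises place, and the effect of an unstated normalisation cannot be judged.

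A second reply is that the effect may be small. This also stands. A difference in room air may well move ions together, and then even 0.5 SD gives only 0.57-0.67. The inflation of 0.033 on top of a real signal is less than the standard error of one test AUC of 0.757 with 60 vs 60 (0.044 by the Hanley-McNeil formula).

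Two stronger readings are tempting. A reader might infer that the test AUC will be inflated; the documents support only that it could be. A reader might also infer that calendar date or storage time differs by group. The plan gives one recruitment window for cases and controls (ending "200 healthy participants from July,2022 to March,2023") and one limit for all bags ("The PEEK airbags were carried out to the laboratory within one week"). For these two, all that can be said is that no check of balance is stated.

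Partial safeguards exist but are not planned as such. The severity analysis ("Analyze the correlation between VOCs and clinical disease severity and prognosis") does not rest on the contrast with healthy people. The ILD and sarcoidosis controls may share the clinical setting, but their number, sampling occasion and place in the 400 are not stated.

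**Conclusion.** The point holds as a conditional one. Occasion is tied to participant type, room air is inhaled, the ambient samples have one stated use, and the random split gives the test set whatever setting difference the discovery set has. A difference, if it exists, could be read as disease, and blinding and splitting would not reveal it.

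Its size is unknown. For ten shifted ions and no disease effect, the assumed cases run from near chance (0.51-0.61 at 0.2-0.3 SD), through a modest 0.57-0.67 (0.5 SD, correlated ions), to about 0.8 (0.5 SD, independent ions). More ions or larger shifts would raise these values; normalisation might lower them. This is a worthwhile, inexpensive improvement to the analysis, with medium confidence. It is not a demonstrated bias.

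**What to change.** Keep the primary analysis and add:

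- (a) A table of collection place, collection date and collection-to-analysis time by group.
- (b) After the primary test-set results are locked, run the ambient samples through the same ion extraction. Compare them ion by ion, at the selected ions, between case-sampling and control-sampling places. If place was not recorded, use days that served one group only, judged from all 400 participants. Discovery participants alone would mislabel days: under even accrual over an assumed 195 collection days, about 40% of days labelled case-only would also have served a validation or test control (63% at 100 days, 31% at 270). Report the number of ambient samples.
- (c) As a sensitivity analysis, extend the ambient comparison to all ions, drop those that differ, refit in discovery, and report that test AUC beside the primary one, labelled as done after the lock.
- (d) Report bronchiectasis versus ILD/sarcoidosis separately, if those controls were sampled in the same clinical setting.

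If the ambient spectra, or their link to place or day, were not kept, state that environmental confounding of the test AUC cannot be excluded.

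The cost is analysis time and no new participants, provided the spectra and records were kept, which the documents do not confirm. A screen at p<0.05 drops about 5% of unaffected ions by chance (0.05 × 290 = 14.5), and the sensitivity AUC may be lower. Power is weak with few samples. Assuming 20 ambient samples per group and correct labels, a Bonferroni test at the selected ions flags a 1 SD ambient difference in 79-100% of runs, but a 0.5 SD difference in only 27-49%. A null result from few samples is therefore not reassurance.

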### **VOCs detection:**

On the HPPI-TOFMS detection platform, soft ionization was achieved by a commercial VUV-Kr lamp with a photon energy of 10.6 eV to predominantly produce radical cations ( $M^+$ ) which are formed as  $M + h\nu \rightarrow M^+ + e$ , which can ionize most VOCs in the breath sample. Meanwhile, some protonated ions are also produced. The VOCs with mass-charge ratio( $m/z$ ) in the range of [20, 320] were detected on HPPI-TOFMS. In this study, the area of the strongest peak in the range of  $[x-0.5, x+0.5]$  was calculated, normalized, and regarded as the feature of VOC with  $m/z$  of  $x$ . Thus, three hundred kinds of VOC ions features were extracted via breath detection in HPPI-TOFMS.

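### Breath bags may reach the laboratory at any time within a week, and nothing in the plan matches or accounts for holding time or run day between bronchiectasis cases and controls

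*Combined protocol and SAP*

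**What the plan says.** The Exhaled Breath collection section contains the one timing rule: "The PEEK airbags were carried out to the laboratory within one week and analyzed by HPPI". Read literally, the week limits carriage to the laboratory; no separate limit is set on the time to analysis. The document gives no storage conditions and does not require fill or analysis times to be recorded.

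The same section says that "All exhaled breath samples were collected by trained investigators following the same protocol", and "For each day of sample collection, ambient air was collected to make sure the environment was not polluted". For the laboratory stage, the Study plan says only that "VOCs were detected by mass spectrometry according to the standard processing flow", without describing that flow.

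The groups are sampled on different occasions. For patients: "The exhaled gas of admitted patients was collected on the day of admission, that of outpatients on the day of outpatient service". For healthy controls: "that of examinees on the day of physical examination".

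Under VOCs detection, the area of the strongest peak around each mass-to-charge value "was calculated, normalized, and regarded as the feature of VOC with" that value; the normalisation method is not given. Under VOCs analysis, ions are selected in three steps: a between-group screen at p = 0.05, a correlation filter at 0.9, and a random forest ranking that keeps ten ions. Neither holding time nor run day appears in any step. The Study plan splits 400 participants (200 cases, 200 healthy) 5:2:3 into discovery, internal validation and blinded test sets.

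**The concern.** The features are peak areas measured after an interval that may vary by days from bag to bag. If some ions decay or accumulate in the bag, their measured level depends on bag age as well as on the participant. If bag age or run day also differs between cases and controls, a handling difference looks like a disease difference to the screen and to every later model.

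The collection occasions give a route by which this could happen: wards and clinics on one side, physical-examination sessions on the other. The blinded test set offers no protection, because random splitting reproduces in it whatever handling difference exists in the full 400. At stake is whether the test-set AUC can be read as discrimination of bronchiectasis.

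**Working it through.** The document states no stability data, holding times or drift rates, so there is no figure to reproduce. The check has two parts: a reading of the safeguards, and an illustration on assumed values.

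**1. What each nearby safeguard covers**

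| Provision | Covers | Equalises bag age or mixes groups in a run? |
|---|---|---|
| Common collection protocol (Exhaled Breath collection) | Sampling | Not stated |
| Daily ambient air sample (same section) | Pollution where samples are collected | No; not described as a stored-bag blank |
| Normalisation (VOCs detection) | Peak areas, method not given | Not stated |
| Laboratory processing flow (Study plan) | Named, content not given | Not stated |
| Evaluator blinding (Study Description) | Evaluation | No |

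**2. Set sizes.** 400 × 0.5, 0.2 and 0.3 = 200, 80 and 120. If each group splits evenly (assumption), discovery has n = 100 per group and the blinded test set 60 per group.

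**3. Chance that a storage-only shift passes the screen.** Take an ion with no disease signal and a group shift of d SD due to storage. By a normal approximation (not the exact Mann-Whitney test), P(pass) ≈ Φ(d/√(2/n) − 1.96), and the single-ion AUC is Φ(d/√2). With n = 100, √(2/100) = 0.1414. For d = 0.3: 0.3/0.1414 = 2.121; 2.121 − 1.96 = 0.161; Φ(0.161) = 0.564.

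| Assumed shift d (SD) | P(pass) | Single-ion AUC |
|---|---|---|
| 0 | 5% | 0.50 |
| 0.2 | 29% | 0.56 |
| 0.3 | 56% | 0.58 |
| 0.4 | 81% | 0.61 |
| 0.5 | 94% | 0.64 |

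**4. The same in days.** Let r be the drift in SD per day, Δ the difference in mean holding time, and 1.5 days the within-group SD of holding time (all assumed). Then d = rΔ/√(1 + (1.5r)²), and both tails are counted. For r = 0.1 and Δ = 3: d = 0.3/√1.0225 = 0.297.

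| Δ (days) | r = 0.05 | r = 0.1 | r = 0.2 |
|---|---|---|---|
| 0 | 5% | 5% | 5% |
| 1 | 6% | 11% | 27% |
| 2 | 11% | 29% | 77% |
| 3 | 18% | 56% | 98% |

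**5. Equal mean holding time.** With Δ = 0, storage produces no group shift: pass rate 5%, AUC 0.50 for a null ion. For an ion with a true effect, variable storage dilutes it by 1/√(1 + (1.5r)²). At r = 0.2 this is 1/√1.09 = 0.958, so a true 0.5 SD becomes 0.479 SD and the single-ion AUC falls from 0.638 to Φ(0.479/√2) = 0.633.

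**6. How much a single bag might change.** The fraction left is 0.5^(days/half-life). From day 1 to day 7 it goes from 79% to 20% for a 3-day half-life, 91% to 50% for 7 days, and 99% to 92% for 60 days (all assumed). These figures compare two individual bags; bias depends on the difference between the groups.

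**The case against.** The strongest reply is that no imbalance has been demonstrated. There is one recruiting hospital, one recruitment period (July 2022 to March 2023), one collection protocol and one carriage limit for everyone. A different collection occasion does not imply separate transport or separate run days; bags from both groups may have travelled and been run together. Normalisation might remove some common storage loss, and the laboratory's processing flow may contain run-order rules in a document that is not part of this one. Also, the document is dated July 17, 2023, after the planned recruitment window closed, so changes to scheduling are probably too late.

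All of this stands as a limit on the claim. In particular, three stronger readings that a reader might infer are not supported:

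- That cases and controls did form separate batches with different waiting times. The document says only that the collection occasion differed.
- That every ion that changes in the bag passes the screen. The pass rates above run from 6% to 98% depending on assumed drift and assumed imbalance, and two further selection steps follow.
- That the AUC partly measures storage in any case. When holding time and run day are unrelated to group, storage adds noise and pulls the AUC down; it does not become a discriminating signal.

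What the reply does not remove is the gap itself. No provision in the document shows that the groups were handled alike after collection, and no planned analysis would reveal it if they were not.

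**Conclusion.** The concern holds in conditional form. The plan leaves bag age and run day uncontrolled and unanalysed, and the different sampling occasions make a group difference possible. If one exists, unstable ions can enter the panel and the blinded test set will not expose them. A storage-only shift of 0.3 SD would pass the screen about 56% of the time, with a single-ion AUC of about 0.58. If none exists, the cost is noise, which is small for a single ion in the example worked here.

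The sizes rest on assumed shifts, drift rates and holding-time spread, an even split of groups across the sets, and a normal approximation. How many of the ten ions might be storage-related cannot be computed from the document. This should be addressed because a simple tabulation would largely settle it and the answer changes what the AUC can support; it is not evidence that the result is biased.

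**What to change.** **For any bags not yet run:** interleave bronchiectasis and control bags in each instrument run, in an order unrelated to diagnosis, within one common holding window, and record fill and analysis times.

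**For bags already run:**

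1. Take the fill date from the visit day, to which the Study plan ties collection, and the analysis date from laboratory records (assumed to exist). Tabulate holding time and run day by group.
2. If the groups are alike on both, report the table; no further analysis is needed.
3. If they differ, repeat ion selection with each ion adjusted for holding time and run day in the discovery set. Report the blinded-test AUC among cases and controls with overlapping holding times beside the main AUC.
4. If there is little overlap, or the times were not recorded, state that the AUC cannot be separated from sample handling. Adjustment cannot rescue runs that contain only one group.

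**Cost:** less flexible scheduling for remaining bags; retrieval of dates, one table and, if needed, one repeat selection and one subset analysis. Some candidate ions may be lost, and the subset AUC will be less precise than one from the full blinded test set of 120. No participants or procedures are added.
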